#### **8.4.4 Cerebral lesion analysis by DWI-NMR 1 day after CEA and correlation to neurological status**

Cerebral lesions: Number of cerebral lesions in perfusion area of carotid artery stenosis assessed at Visit 5 by the central reading lab ([name], Tübingen).

- back
- front right
- front left
- and total

Groups will be compared for

- change of number of DWI lesions V5 compared to V1 (delta number of lesions)
- percent change of number of DWI lesions V5 compared to V1

using ANOVA.

In addition groups will be compared for

- rate of incidence of patients with DWI lesions after treatment (V5)
- rate of incidence of patients with new DWI lesions after treatment (V5)
- rate of patients with DWI lesions in V5 reduced compared to V1

using Fisher's exact test.

Neurological status: Modified Rankin Scale (MRS) assessed at Visit 6:

0	No symptoms at all
1	No significant disability despite symptoms; able to carry out all usual duties and activities
2	Slight disability; unable to carry out all previous activities, but able to look after own affairs without assistance
3	Moderate disability; requiring some help, but able to walk without assistance
4	Moderately severe disability; unable to walk without assistance and unable to attend to own bodily needs without assistance
5	Severe disability; bedridden, incontinent and requiring constant nursing care and attention
6	Dead

The following correlations will be performed by treatment group:

- Cerebral lesions of back area of carotid artery stenosis x MRS
- Cerebral lesions of front right area of carotid artery stenosis x MRS

Statistical Analysis Plan  
Test product: Revacept  
EudraCT number: 2011-001006-10  
Date 10.06.2019

- Cerebral lesions of front left area of carotid artery stenosis x MRS

Correlation analysis will be performed by calculating the Pearson correlation coefficient. In a subgroup analysis, only patients will be compared who did not receive any change in the concomitant medication with anti-platelet activity (=rescue medication) between the initial assessment at V1 and the follow-up investigation at V3 / V5.

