3. STUDY ENDPOINTS

The **efficacy endpoints** are:

- to evaluate whether the incidence of preoperative microembolic signals (MES) is reduced in patients with symptomatic carotid artery stenosis who have been treated with Revacept plus antiplatelet monotherapy (aspirin or clopidogrel) versus antiplatelet monotherapy alone (placebo). MES will be assessed by transcranial Doppler (TCD) examination.(before and after treatment)
- Rate of MES per hour (before and after treatment)
- Assessment of neurological status (NIH Stroke Scale)
- Cerebral lesion analysis by DWI-NMR and correlation to neurological status (before and after treatment)
- Clinical endpoints will be summarised cumulatively i.e. before treatment, one and three days after treatment, at 3 months and at 12 months. The following endpoints will be recorded:
 - Rate of all cause death
 - Rate of stroke-related death
 - Any TIA, amaurosis fugax or stroke including haemorrhagic stroke
- Assessment of cardiovascular outcome including myocardial infarction and re-intervention up to 3 and 12 months

Safety objectives

To assess safety, adverse events will be continuously recorded and be overseen by an independent Data Safety Monitoring Board (see section 1.3).

Safety will be summarised by treatment group and include the following:

- Vital signs
- ECG parameters
- Anti-drug antibody titres
- Reporting AEs including wound healing complications, laboratory abnormalities and use of concomitant medication
- Haemostasis will be closely monitored by assessing:
 - laboratory parameters indicating thrombocytopenia and bleeding according to the RE-LY study group criteria
 - where feasible: in vitro platelet function with collagen, TRAP and ADP-mediated platelet aggregation and in vitro bleeding time by PFA-100 / PFA-200

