7.2.9. DWI-NMR

The following parameters will be recorded:

- Occurrence of new cerebral lesions from baseline (visit 1) to visit 5
- If possible, number of new cerebral lesions developed between baseline (visit 1) and visit 5

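### SAP 8.4.4 never analyses the number of new DWI lesions named in protocol 7.2.9; its only count comparisons are net and percent change, which mix new lesions with lesions that have disappeared

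*SAP*

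**What the plan says.** Protocol 7.2.9 lists two DWI parameters. The first is unconditional: "Occurrence of new cerebral lesions from baseline (visit 1) to visit 5". The second is conditional: "If possible, number of new cerebral lesions developed between baseline (visit 1) and visit 5".

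SAP 8.4.4 defines its lesion variable as "Number of cerebral lesions in perfusion area of carotid artery stenosis assessed at Visit 5 by the central reading lab", by region and in total. It plans:

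- by ANOVA, "change of number of DWI lesions V5 compared to V1 (delta number of lesions") and the percent change between the same visits;
- by Fisher's exact test, the rates of patients with any lesion at Visit 5, with new lesions at Visit 5, and "rate of patients with DWI lesions in V5 reduced compared to V1";
- by treatment group, correlations of the three regional lesion counts with the modified Rankin score at Visit 6: "Correlation analysis will be performed by calculating the Pearson correlation coefficient".

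SAP 8.4 provides ANOVA for numerical data, with a Wilcoxon sensitivity analysis if normality fails. SAP 8.2.9 groups baseline lesion counts into classes, the first of which is zero. For the correlation, protocol section 3 asks only for "Cerebral lesion analysis by DWI-NMR and correlation to neurological status (before and after treatment").

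**The concern.** The protocol's count is of lesions that arise between the two scans. The SAP's count is a difference between two totals, and the two agree only if every Visit 1 lesion is still visible at Visit 5. Patients enter within 30 days of a TIA, amaurosis fugax or stroke, so some will have lesions from the qualifying event at Visit 1. The SAP's own reduced rate presupposes that counts can fall.

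Three things follow. Disappearance of old lesions adds variation unrelated to whether treatment prevents new ones. The same patient can appear as a success on one line of the DWI table and as an event on another. And the conditional protocol parameter drops out with no stated reason, so a reader of the report cannot tell whether counting was impossible or was simply not done.

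The correlation raises a smaller, separate matter. Counts at Visit 5 include lesions already present at Visit 1, and Pearson's coefficient is applied to skewed counts against an ordinal 0–6 score.

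**Working it through.** **No plan figure to reproduce.** The documents give no power, effect size or variance for DWI.

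**Identity.** Visit 5 count = Visit 1 count − disappeared + new, so net change = new − disappeared.

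| Visit 1 | Disappeared | New | Visit 5 | Net change | Percent change | Reduced? | New lesion? |
|---|---|---|---|---|---|---|---|
| 5 | 4 | 2 | 3 | −2 | −40% | yes | yes |
| 2 | 2 | 1 | 1 | −1 | −50% | yes | yes |
| 1 | 1 | 1 | 1 | 0 | 0% | no | yes |
| 0 | 0 | 2 | 2 | +2 | undefined | no | yes |

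The first two rows are scored reduced despite new lesions. In the third, net change hides a new lesion. In the fourth, percent change cannot be computed. This part needs no assumption about rates.

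**Size, on assumed inputs.** The 50 per arm is from SAP 3.3. Everything else is assumed: new lesions negative binomial with means 1.0 and 0.4, dispersion 0.5; Visit 1 lesions negative binomial with mean m = 1 or 3, dispersion 0.7; each Visit 1 lesion disappears with probability p, equal in both arms; two arms compared, two-sided 5%.

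Variances:

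- New lesions: mean + mean²/0.5, giving 1.0 + 2.0 = 3.00 and 0.4 + 0.32 = 0.72. The sum is 3.72.
- Disappeared lesions, per arm: p(1−p)m + p²(m + m²/0.7).
  - m = 1: 0.43 at p = 0.3; 0.86 at p = 0.5.
  - m = 3: 2.06 at p = 0.3; 4.71 at p = 0.5.

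The expected difference is 0.6 on either measure, because disappearance is the same in both arms. Only the standard error changes. Approximate power is Φ(0.6/SE − 1.96):

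| Measure | SE | Approximate power |
|---|---|---|
| New lesions | √(3.72/50) = 0.273 | 59% |
| Net change, m = 1, p = 0.3 | √((3.72 + 2×0.43)/50) = 0.303 | 51% |
| Net change, m = 1, p = 0.5 | √((3.72 + 2×0.86)/50) = 0.330 | 44% |
| Net change, m = 3, p = 0.3 | √((3.72 + 2×2.06)/50) = 0.396 | 33% |
| Net change, m = 3, p = 0.5 | √((3.72 + 2×4.71)/50) = 0.513 | 22% |

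Simulation agrees. ANOVA on new lesions has about 60–64% power. ANOVA on net change has about 43–50% at m = 1 and 21–32% at m = 3 over this range of p. At p = 0 the two measures are identical. The Wilcoxon test on new lesions has about 50–53%.

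**Misclassification.** Among simulated patients with at least one new lesion, the share scored reduced at 30–50% disappearance is 3–7% at m = 1 and 15–25% at m = 3. It is zero if nothing disappears.

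**Correlation.** In an illustration with one planted patient (20 lesions, Rankin 5) among 49 unrelated pairs, Pearson's coefficient reached p < 0.05 in 44% of samples in one run and 53% in another. Spearman's did so in 6%. This shows sensitivity to a single patient only; the SAP names no significance test for the correlation.

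**The case against.** The strongest reply is that new lesions are analysed. The protocol's unconditional parameter, new lesion yes or no, is compared by Fisher's exact test beside the reduced rate, and the count is required only if possible. This stands as far as it goes: a reader might infer that the SAP drops new lesions altogether, and it does not. But the qualifier excuses scans that cannot be counted. It does not explain the absence of any count analysis or of any statement that counting failed.

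A second reply is that the loss depends on unsupported inputs. That also stands. The documents give neither lesion counts nor disappearance rates; TIA and amaurosis fugax patients are eligible, so baseline counts may be low; and the in-patient part of the trial lasts about six days. The large losses belong to a Visit 1 mean of 3 with 30–50% disappearance and should not be quoted alone.

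Third, a reader might take the correlation as a departure from the protocol. It is not. Protocol section 3 does not restrict it to new lesions, and total lesion burden against three-month disability is a legitimate descriptive question. Even the use of Visit 5 counts is inferred from the lead-in to SAP 8.4.4, because the correlation bullets give no visit.

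Fourth, it is tempting to replace ANOVA by Wilcoxon, to delete the reduced rate, or to redefine the correlation as new lesions against Rankin change. The first is not supported by the calculation: ANOVA on new lesions does better here than Wilcoxon, and SAP 8.4 already has Wilcoxon as a sensitivity analysis. The other two are matters of preference.

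Finally, the study is exploratory. That limits the weight of the point but does not remove it, since these comparisons will still be run and reported.

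**Conclusion.** The concern holds in a limited form. One protocol parameter, the number of new lesions, has no analysis in SAP 8.4.4 and no reason is given. The two count comparisons that stand in its place measure something else: net change is diluted whenever Visit 1 lesions disappear, percent change is undefined at a Visit 1 count of zero, and patients with new lesions can be scored as reduced. These statements follow from the text and from arithmetic.

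The size does not. Under the assumptions above, power on net change falls from about 60–64% to about 43–50% or 21–32%, depending on the Visit 1 mean, and there is no loss without disappearance. The documents do not show which setting applies.

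The correlation is a design weakness, not a protocol departure. That it mainly reflects the severity of the qualifying stroke is something a reader might infer, but the documents give nothing to quantify it.

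**What to change.** In SAP 8.4.4:

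- Make the number of new lesions at Visit 5 the main count comparison, with new lesions identified by comparing the Visit 5 image with the Visit 1 image and not by subtracting totals. Use the existing ANOVA with its Wilcoxon sensitivity analysis. State for which scans counting was not possible.
- Label net change, percent change and the reduced rate as supplementary. Cross-tabulate reduced against new lesions, and say how percent change is handled when Visit 1 shows none.
- For the Rankin correlation, use Spearman's coefficient, state that Visit 5 counts include lesions already present at Visit 1, and add the total and the new-lesion count as correlates.

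If the central reader already identified new lesions by image comparison for the planned new-lesion rate, this costs SAP wording only. The SAP does not define how a lesion is judged new, so this should be confirmed with the reading laboratory; if it was derived from the regional totals, a re-read would be needed. A small downside is that scans in which new lesions could not be counted contribute only the yes/no item.

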7.1.5. Visit 5: 24 hrs after CEA or other intervention (\pm 24 hrs)

- Physical examination/ vital signs
- Review of concomitant medication
- Assessment of AEs including wound healing complications
- Assessment of clinical outcome
- ECG examination
- Assessment of interventional outcome and NIHSS
- Cerebral DWI-NMR post intervention (12-72 hrs after intervention)
- clinical biochemistry, clinical haematology (incl. assessment of bleeding according to RE-LY study group criteria), coagulation and urinalysis

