7.1.6. Visit 6: follow up 3 months after treatment (\pm 1 month)

- Physical examination/ vital signs
- Review of concomitant medication
- Assessment of AEs including wound healing complications
- Assessment of neurological status (MRS, Barthel Index, NIH Stroke Scale)
- Assessment of clinical outcome
- ECG examination
- clinical biochemistry, clinical haematology (incl. assessment of bleeding according to RE-LY study group criteria), coagulation and urinalysis
- in vitro bleeding time PFA100 /PFA200 and platelet aggregation assay (response to collagen, ADP and TRAP)
- Pharmacokinetic blood sampling (for approximately 20 % of patients)
 - **T3m** 3 months (\pm 1 month) after IMP infusion
- detection of anti-Revacept antibodies

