### 8.4.3 Assessment of neurological status (NIH Stroke Scale)

The neurological status was assessed at Visit 2, Visit 5, and Visit 6 by the NIH stroke scale. It comprises 15 items.

1a	Level of Consciousness		0	1	2	3		
1b	LOC Questions		0	1	2			
1c	LOC Commands		0	1	2			
2	Best Gaze		0	1	2			
3	Visual		0	1	2	3		
4	Facial Palsy		0	1	2	3		
5a	Motor Arm	left arm	0	1	2	3	4	9
5b		right arm	0	1	2	3	4	9
6a	Motor Leg	left leg	0	1	2	3	4	9
6b		right arm	0	1	2	3	4	9
7	Limb Ataxia		0	1	2			
8	Sensory		0	1	2			
9	Best Language		0	1	2	3		
10	Dysarthria		0	1	2			
11	Extinction and Inattention		0	1	2			
Total Score			Maximum = 62					

with rating options on the scale 0, 1, 2, 3, 4 and 9 depending on the single item.

Frequencies of scale values will be summarized by visit and by item. Comparison between groups will be performed using the Mantel-Haenszel Chi-square test.

The total score of the NIH Stroke Scale will be compared between groups by visit using ANOVA.

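### SAP 8.4.4 relates right-skewed lesion counts to the ordinal Rankin score by Pearson's coefficient alone, so one extreme patient can dominate a small exploratory estimate; a rank correlation should lead.

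*SAP*

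**What the plan says.** Protocol section 3 lists the endpoint "Cerebral lesion analysis by DWI-NMR and correlation to neurological status (before and after treatment"). That bullet names no scale. A separate bullet reads "Assessment of neurological status (NIH Stroke Scale").

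SAP 8.4.4 carries out the correlation as follows:
- **Lesions:** counts in the back, front right and front left areas, "assessed at Visit 5 by the central reading lab". The section also lists a total count, but does not correlate it.
- **Neurological status:** "Neurological status: Modified Rankin Scale (MRS) assessed at Visit 6", scored 0 to 6 with 6 meaning dead. Protocol 7.1.6 places this visit about a quarter of a year after dosing: "Visit 6: follow up 3 months after treatment".
- **Method:** "Correlation analysis will be performed by calculating the Pearson correlation coefficient", separately by treatment group.

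No rank correlation, outlier check or confidence interval is specified for these coefficients. The fallback to the Wilcoxon test in SAP 8.4 is a sensitivity analysis for group comparisons made by ANOVA and does not apply to a correlation.

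NIHSS is available at the DWI visit. SAP 8.4.3 states "The neurological status was assessed at Visit 2, Visit 5, and Visit 6 by the NIH stroke scale", and protocol 7.1.5 schedules "Assessment of interventional outcome and NIHSS" at Visit 5. The Rankin score is scheduled only at Visits 2 and 6.

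**The concern.** Pearson's coefficient measures linear association and weights each patient by the product of two deviations from the mean. It suits two roughly symmetric continuous measures. Here one variable is a count with a long right tail: the SAP's own baseline classes (8.2.9) run 0, 1, 2, 3-5, 6-10 and over 10. The other is a short ordinal scale. In an arm of at most 50, fewer if scans or Visit 6 scores are missing, a single patient who is extreme on both can supply much of the coefficient.

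This is the only analysis planned for the correlation endpoint. An exploratory study is read through its estimates, so a reader could take one patient's result for a pattern in the arm.

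There is a separate and lesser point about timing. Lesions are counted at Visit 5 and disability is scored at Visit 6. Events between the two visits enter the Rankin score, and the scale gives death the value 6. The coefficient therefore mixes the immediate effect of the lesions with whatever happened later.

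**Working it through.** The documents give no expected correlation, power or precision for this analysis, so there is no figure to reproduce. The check asks how far one patient can move each coefficient.

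**Inputs from the documents:** Pearson, Visit 5 counts, Visit 6 Rankin, analysis by arm (SAP 8.4.4); 50 per arm (SAP 3.3); open-ended count classes (SAP 8.2.9). **Assumed:** the distributions below and a two-sided 5% level.

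**1. Constructed example.** Take 49 patients in seven blocks of seven. The Rankin score is constant within a block (0, 0, 1, 1, 2, 2, 3), and each block has lesion counts 0, 0, 0, 0, 0, 1, 2. Then Σx = 21, Σx² = 35, Σy = 63, Σy² = 133, Σxy = 27. The covariance term is 27 − 21 × 63/49 = 0, so r = 0.

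Add one patient with 6 lesions and Rankin 5 (n = 50):
- Sxx = 71 − 27²/50 = 56.42
- Syy = 158 − 68²/50 = 65.52
- Sxy = 57 − 27 × 68/50 = 20.28
- r = 20.28/√(56.42 × 65.52) = 0.33, p = 0.018 (critical |r| at n = 50 is 0.279)

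With 11 lesions instead: Sxx = 156 − 32²/50 = 135.52, Sxy = 82 − 32 × 68/50 = 38.48, r = 0.41, p = 0.003. Spearman's coefficient is 0.08 (p = 0.60) in both cases, because the added patient simply holds the top rank.

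**2. Simulation, no true association, n = 50 including the one extreme patient.** Counts are negative binomial with mean m and dispersion k. Rankin shares are 30/30/20/12/6/2/0% for scores 0 to 6.

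| Counts | Added patient | Mean Pearson r | Mean Spearman |
|---|---|---|---|
| m = 1.5, k = 0.3 | 6 lesions, Rankin 5 | 0.09 | 0.06 |
| m = 1.5, k = 0.3 | 11 lesions, Rankin 5 | 0.17 | 0.06 |
| m = 1.5, k = 0.3 | 30 lesions, Rankin 5 | 0.30 | 0.06 to 0.07 |
| m = 1.5, k = 0.3 | 30 lesions, Rankin 2 | 0.06 | 0.03 |
| m = 0.5, k = 0.5 | 6 lesions, Rankin 5 | 0.24 | 0.08 |
| m = 1, k = 0.5 | 6 lesions, Rankin 5 | 0.15 | 0.07 |
| m = 2, k = 0.5 | 6 lesions, Rankin 5 | 0.07 | 0.05 |

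The top of the Pearson range, 0.36, comes from 30 lesions with Rankin 5 at m = 0.5, k = 0.5. For 6 lesions with Rankin 5 and k = 0.5, Pearson reaches p < 0.05 in 6% to 35% of runs, against 5% to 8% for Spearman.

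**3. Without an extreme patient.** At m = 1.5, k = 0.3 both coefficients average 0.00 with a standard deviation of about 0.145. Test size is about 5% for each.

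**4. How likely is the extreme patient?** At m = 1.5, k = 0.3 the chance of 30 or more lesions is about 0.0004 per patient, or 1 − (1 − 0.0004)^50 ≈ 2% for any such patient in an arm. The median largest count in 50 patients is 13. The same patient must also have a poor Rankin score.

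**The case against.** The best case for leaving the plan alone has four parts.

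- **The extreme patient is put in by hand.** This stands as a limit on size. A coefficient near 0.3 needs a rare count together with Rankin 5, or counts that are otherwise very low. With 30 lesions but Rankin 2 the mean is only 0.06. A reader might take 0.3 as the typical distortion; the calculations do not support that.
- **Pearson's test keeps its size.** This also stands. The gain from ranks is a steadier estimate. No inflated error rate has been shown for the case without an extreme patient.
- **Rankin is a legitimate choice.** A reader might infer that the SAP departs from the protocol by not using NIHSS. The documents do not support this. The NIHSS wording belongs to a different endpoint bullet, the correlation bullet names no scale, and protocol 7.1.2, 7.1.6 and Appendix A all place the Rankin scale under neurological status. Relating early lesions to disability at 3 months is a sensible question.
- **Nothing confirmatory depends on it.** This stands. The coefficients are computed within arms. Lesion differences between arms are tested separately in the same section by ANOVA and Fisher's exact test, and all tests are exploratory.

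A reader might also infer that the gap between Visits 5 and 6 causes the sensitivity to one patient. It does not. That sensitivity comes from applying Pearson to a skewed count and an ordinal score. NIHSS is itself ordinal and likely to be skewed, so changing the scale or visit would not cure it.

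None of this gives a reason to prefer Pearson as the only coefficient.

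**Conclusion.** The point holds as a minor one. Pearson's coefficient is poorly matched to these two variables, and the SAP offers no rank-based alternative for the only analysis of the correlation endpoint. With no true association, one patient with 6 to 30 lesions and Rankin 5 shifts the mean Pearson r to about 0.07 to 0.36, against about 0.05 to 0.08 for Spearman. The range rests on assumed count and Rankin distributions, since the documents give none, and the effect shrinks as counts become more widely spread. The omission of the total count and the absence of a same-visit correlation are separate, smaller gaps. There is no contradiction of the protocol and no effect on any comparison between treatment groups.

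**What to change.** In SAP 8.4.4, before unblinding:

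1. Name Spearman's rank correlation with a 95% confidence interval as the main coefficient. Pearson may stay beside it. In SAS this is an option in the same procedure. The price is some loss of power if a real association is carried by the high counts.
2. Add the total lesion count, which the section already lists, as a further row.
3. As a supplementary analysis, add the correlation of Visit 5 lesions with Visit 5 NIHSS, also by Spearman, and keep Rankin at Visit 6. The data are already collected, so the cost is a few more output rows. SAP 8.4.3 allows item codes of 9 and a total of up to 62, so state how those codes are handled before the total is used.
4. State how deaths before Visit 6 enter the Rankin correlation.

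No new data, visits or patients are needed.

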#### **8.4.5 Clinical endpoints summarised cumulatively i.e. before treatment, before CEA, 1 day after CEA, at 3 months and at 12 months.**

For the following endpoints

- Rate of all cause death
- Rate of stroke-related death
- Any TIA or stroke including haemorrhagic stroke
- Rate of Myocardial infarctions and coronary re-intervention

the number of patients will be summarized by means of frequency tables. Groups will be compared using Fisher's exact test.

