Version 7.1 (15.04.2013)	
Substantial changes:
 
 Section synopsis, Fehler! Verweisquelle konnte nicht gefunden werden., 7.2.6 and Appendix A: Amaurosis fugax assessed as secondary endpoint Section synopsis, 5.2.1 and 6.1.7: 
 European Carotid Surgery Trial (ECST) criteria used for grading of carotid stenosis (instead of North American Symptomatic Carotid Endarterectomy Trial criteria) Patients with Amaurosis fugax (subgroup of TIA) included in study population Flow velocity not assessed as inclusion criterion Section 7.2.10: Troponin may be determined instead of CK 
Non-substantial changes:
 
 Section 1.3: Change of address of DSMB member Section synopsis and 5.1: Wording 'carotid endarterectomy' changed to more general definition of intervention Section synopsis, 5.2.1 and 6.1.7: 
 Wording of exclusion criterion haemorrhagic transformation corrected Section synopsis, 7.1 and 7.2.5: Wound healing complications included in general assessment of adverse events Section 7.2.7: Change of address of TCD core lab Several locations throughout document: 
 thrombocyte function may be analysed by PFA-100 or newer PFA-200 device
Version 7.2 (08.08.2013)	
Non-substantial change:
 
 Section 8.3.1: Update of SAE fax number
Version 7.3 (12.09.2013)	
 Section 8.1 and 8.3.1: SAE, SAR and SUSAR reporting period for PIs set to 24 hours.
Version 7.4 (22.07.2014)	
 Section Synopsis and 5.2.2: Modification of eligibility criteria. Section 1.3: Change of DSMB meeting interval
Version 8 (22.06.2015)	
Change to exploratory study design due to low incidence of MES (i.e. high screening failure rates) upon recommendation by the DSMB (section Synopsis, section 3, 5 and 9 and minor changes for consistency throughout document).

SYNOPSIS

Name of Sponsor:
 
advanceCOR GmbH [name] [name] Germany
	
Coordinating Investigator:
 
PD Dr. med. [name] Department of Neurology TU München [name] [name] Germany

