5.2.1. Inclusion Criteria

For entry into the study, the following criteria **MUST** be met:

1) Signed written informed consent

2) Target population

a) Diagnosis:

- Extracranial carotid artery stenosis (diagnosed by vascular duplex ultrasound peak flow or angiography)
 - Lesions with $\geq 50\%$ stenosis according to the European Carotid Surgery Trial (ECST) criteria
- TIA, amaurosis fugax or stroke within the last 30 days

b) Age and sex: Men and women aged >18 years

Women of childbearing potential (WOCBP) must be using an adequate method of contraception to avoid pregnancy throughout the study and for up to 4 weeks after receiving investigational product in such a manner that the risk of pregnancy is minimised.

WOCBP include any female who has experienced menarche and who has not undergone successful surgical sterilisation (hysterectomy, bilateral tubal ligation, or bilateral oophorectomy) or is not postmenopausal. Post menopause is defined as:

- Amenorrhea ≥ 12 consecutive months without another cause or
- For women with irregular menstrual periods and on hormone replacement therapy (HRT), a documented serum follicle stimulating hormone (FSH) level > 35 mIU/mL

Women who are using oral contraceptives, other hormonal contraceptives (vaginal products, skin patches, or implanted or injectable products), or mechanical products such as an intrauterine device or barrier methods (diaphragm, condoms, spermicides) to prevent pregnancy, or are practicing abstinence or where their partner is sterile (e.g. vasectomy) should be considered to be of childbearing potential. WOCBP must have a negative serum or urine pregnancy test (minimum sensitivity 25 IU/L or equivalent units of HCG) within 72 hours prior to the start of study intervention.

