7.2.6. Clinical Outcome

Clinical outcome will be summarised cumulatively i.e. before treatment, one and three days after treatment at 3 months and at 12 months. See Appendix B for definitions of clinical events. The following endpoints will be recorded:

- Rate of all cause death
- Rate of stroke-related death
- Any TIA, amaurosis fugax or stroke including haemorrhagic stroke,
- Assessment of cardiovascular outcome including myocardial infarction and re-intervention up to 3 and 12 months

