## 4. STUDY VARIABLES

### 4.1 Efficacy endpoints

- to evaluate whether the incidence of preoperative microembolic signals (MES) is reduced in patients with symptomatic carotid artery stenosis who have been treated with Revacept plus antiplatelet therapy (aspirin or clopidogrel) versus antiplatelet therapy alone (placebo) prior to carotid endarterectomy (CEA) or carotid artery stenting.  
MES was assessed by transcranial Doppler (TCD) examination (before and after treatment).
- Rate of MES per hour (before and after treatment)
- Assessment of neurological status (NIH Stroke Scale)
- Cerebral lesion analysis by DWI-NMR and correlation to neurological status (before and after treatment and CEA or stenting)
- Clinical endpoints will be summarised cumulatively i.e. before treatment, one and three days after treatment, at 3 months and at 12 months. The following endpoints will be recorded:
  - Rate of all cause death
  - Rate of stroke-related death
  - Any TIA or stroke including haemorrhagic stroke
- Assessment of cardiovascular outcome including myocardial infarction and re-intervention up to 3 and 12 months
- Combined clinical endpoints for ischemic events (myocardial infarction and ischemic stroke/TIA) and rate of rescue medication (additional anti-platelet co-medication) during the study

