#### **8.4.6 Ischemic events and rate of rescue medication during the study**

Combined clinical endpoints for ischemic events (myocardial infarction and ischemic stroke/TIA) and rate of rescue medication (additional anti-platelet co-medication) during the study will be analyzed comparing groups for

- incidence of events adjusted for application of rescue medication during the study (yes/no)

using the Cochran-Mantel-Haenszel procedure.

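### SAP 8.4.5 limits re-intervention to coronary procedures, against the protocol and the SAP's own endpoint list, and leaves unstated whether amaurosis fugax counts as TIA

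*SAP*

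**What the plan says.** **Re-intervention.** Protocol 7.2.6 lists "Assessment of cardiovascular outcome including myocardial infarction and re-intervention up to 3 and 12 months". The synopsis and section 3 carry the same item, as do SAP 2 and 4.1. None of these five places names a vascular bed. SAP 8.4.5, the only section that says how the item will be analysed, reads "Rate of Myocardial infarctions and coronary re-intervention".

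**Cerebral events.** Protocol 7.2.6, section 3 and the synopsis list "Any TIA, amaurosis fugax or stroke including haemorrhagic stroke". SAP 2, 4.1 and 8.4.5 list "Any TIA or stroke including haemorrhagic stroke". Amaurosis fugax is one of the qualifying events for entry in protocol 5.2.1 ("TIA, amaurosis fugax or stroke within the last 30 days") and has its own definition in Appendix B, which defines neither TIA nor re-intervention. The version 7.1 entry in the amendment history describes the change to the population as "Patients with Amaurosis fugax (subgroup of TIA) included in study population" and, under the same version, records "Amaurosis fugax assessed as secondary endpoint".

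**Composite.** SAP 8.4.6 adds an endpoint that combines myocardial infarction with ischaemic stroke or TIA, adjusted for rescue medication. It names neither amaurosis fugax nor any re-intervention. The protocol has no such composite.

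**The concern.** An analysis section should count what the endpoint list promises. Here it narrows one item and leaves another open to interpretation.

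The single word *coronary* takes a whole class of events out of the 3- and 12-month tables. The procedure scheduled at visit 4 is CEA or another intervention, and no coronary procedure is scheduled. A second carotid procedure is therefore an event that readers of this trial would expect to find under re-intervention. A programmer who follows 8.4.5 literally would leave it out.

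For amaurosis fugax the risk is ambiguity. It can bring a patient into the trial, and the protocol lists it beside TIA. Because the SAP never names it, two programmers could each follow the SAP faithfully and report different numbers of patients with a cerebral event.

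**Working it through.** No plan figure needs to be reproduced, because the point concerns endpoint definitions. The check sets the wording side by side.

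| Place | Amaurosis fugax named? | Bed stated for re-intervention |
|---|---|---|
| Protocol synopsis | Yes | None |
| Protocol 3 | Yes | None |
| Protocol 7.2.6 | Yes | None |
| SAP 2 | No | None |
| SAP 4.1 | No | None |
| SAP 8.4.5 (analysis) | No | Coronary |
| SAP 8.4.6 (composite) | No, only TIA | Re-intervention not included |

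1. **Re-intervention.** The restriction appears in 0 of 3 protocol statements, 0 of 2 SAP endpoint lists, and the one SAP analysis statement. SAP 8.4.5 thus differs from the protocol and from SAP 2 and 4.1.

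2. **Is the event picked up in another efficacy analysis?** SAP 8.4.1 to 8.4.4 cover microembolic signals, the NIH Stroke Scale, and diffusion-weighted imaging (DWI) lesions with their correlation to the Rankin scale. SAP 8.4.6 covers infarction, ischaemic stroke and TIA. None includes a re-intervention.

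3. **Do the safety tables catch it?** Not reliably. The protocol 7.1 schedule marks adverse events up to visit 6 at 3 months. Visit 7 at 12 months is a telephone call limited to clinical outcome (7.1.7). Under 8.3.1, routine collection of serious adverse events ends 30 days after dosing; later ones are sought only if related to the product or a protocol-specified procedure. A carotid re-intervention between months 3 and 12 might therefore appear only in the patient listings of SAP 8.7.

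4. **Is the change documented?** SAP 1 says that the plan adds detail to the protocol dated 22.06.2015, whose current text has both endpoints in full. It also provides for documenting changes to principal features that arise from the blind review. Neither document mentions or explains either difference.

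5. **Amaurosis fugax.** It is named in 3 of 3 protocol statements of the event endpoint and in 0 of 3 SAP statements. If it is a kind of TIA, as the amendment history says, it enters 8.4.5 and 8.4.6 through TIA. If it is a separate component, as the protocol's listing and Appendix B could suggest, it does not. The SAP does not choose.

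6. **Size per patient.** The planned arm size is 50 (protocol synopsis, SAP 3.3). SAP 8.4.5 counts patients, so an event matters only if the patient is not already counted on that line. Each such patient adds 1/50 = 0.02, or 2 percentage points, to the arm's rate. The documents give no rate of amaurosis fugax or of re-intervention, so the number of such patients cannot be derived.

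**The case against.** The case for leaving the text alone has four parts.

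- **Re-intervention may have meant coronary all along.** The item stands next to myocardial infarction under cardiovascular outcome, apart from the cerebral events, and no bed is stated. Nor does the protocol use the word intervention only for carotid procedures: 5.2.1 uses it for study treatment and 8.1.1 for medical or surgical measures in general. Restenosis and technical CEA failure in Appendix B are defined by degree of stenosis, not as procedures. All this stands as far as it goes. A reader might infer that the protocol expressly promises a count of carotid re-interventions; it does not. Including them is an inference from unqualified wording in a trial built around a carotid procedure. But a coronary-only meaning is not stated anywhere before 8.4.5, so the restriction still needs either removal or a reason.

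- **Amaurosis fugax is already inside TIA.** This largely stands. A reader might infer that recurrent amaurosis fugax drops out of every efficacy analysis. The documents do not support that, because the only statement of how the two terms relate makes one a subgroup of the other, and listing amaurosis fugax separately is compatible with this. What remains is that the classification sits in an amendment-history entry and the SAP does not repeat it.

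- **The 8.4.6 composite narrows nothing.** Correct. It is new in the SAP, so no protocol endpoint has been cut there. It needs only a statement of what TIA covers.

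- **The study is exploratory.** Also correct. No confirmatory hypothesis is tested (SAP 7.5), and neither item is the leading microembolic-signal endpoint. That lowers the stakes but does not settle which events the tables should contain.

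**Conclusion.** The point holds in two unequal parts. The firm part is that SAP 8.4.5 restricts re-intervention to coronary procedures, in conflict with the protocol and with SAP 2 and 4.1, with no documented reason; as written, a non-coronary re-intervention reaches no efficacy table. The lesser part is that the SAP leaves unstated whether amaurosis fugax counts as TIA.

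The size is unknown. The 2 points per additional patient assume the planned 50 per arm and a patient with no other event on the same line. Any projected number of missed events would rest on rates that the documents do not contain, and if no such events occur the tables do not change. The effect is on which events are counted and on agreement with the protocol; no error rate or decision rule is touched. It should be corrected, but it does not threaten the trial's main analysis.

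**What to change.** Before unblinding:

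- **SAP 8.4.5, re-intervention:** remove the coronary restriction and tabulate re-intervention by vascular bed (carotid, coronary) as far as the CRF records it. If the narrowing was intended, document it as a change from the protocol, with the reason.
- **SAP 2, 4.1 and 8.4.5, cerebral events:** restore the protocol component "Any TIA, amaurosis fugax or stroke including haemorrhagic stroke".
- **SAP 8.4.6:** state whether TIA in the composite includes amaurosis fugax.

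The cost is a wording change and minor table programming. Protocol 7.2.6 says that these outcomes will be recorded, so no new data collection is proposed. The CRF was not available, so whether it separates carotid from coronary re-intervention must be checked; if it does not, report the unqualified total and say so.
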